9.1.4.3. Infusion Set Changes

Patients should change their infusion set and reservoir every 3 days.

The patient's study diary will be used to collect unplanned infusion set changes, including date and time of change and the primary reason for unplanned change.

- Pump occlusion alarm,
- Unexplained high BG,
- Infusion site reaction (pain, redness or swelling at infusion site), or
- Infusion set problem (infusion set kinked, pulled out, leaking, reservoir empty, etc.).

Unexplained hyperglycemia is defined as high BG >300 mg/dL that cannot be explained by a missed prior bolus, dietary indiscretion, rebound or treatment of hypoglycemia, a pump failure, an empty pump reservoir, an infusion set complication (for example, kinked, came out, leaking), or an infusion site complication (for example, pain, redness).

Investigators will review pump occlusion alarms, unexplained hyperglycemia, and unplanned infusion set changes with patients at each visit.

Any interruption of CSII will need to be documented in the eCRF. When patients resume use of pump following the interruption, the infusion set change should not be entered as an unplanned infusion set change in the study diary.

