6.1. General Considerations

Statistical analysis of this study will be the responsibility of Lilly or its designee. Any change to the data analysis methods described in the protocol will require an amendment ONLY if it changes a principal feature of the protocol. Any other change to the data analysis methods described in the protocol, and the justification for making the change, will be described in the SAP or the clinical study report (CSR). Additional exploratory analyses of data will be conducted, as deemed appropriate.

For purposes of analysis, the following populations are defined in [Table ITSM.6.1](#):

Table ITSM.6.1. Patient Populations

Population	Description
Entered	All patients who give informed consent.
Enrolled	All patients who receive at least 1 dose of open-label Humalog in the 2-week lead-in period.
Randomized	All patients who are randomly assigned to study treatment at Visit 4 and receive at least 1 dose of the randomly assigned IP. Treatment will be defined on the basis of the treatment the patients are assigned to.
Pilot	All patients in the pilot safety assessment.

Unless otherwise specified, all efficacy and safety analyses will be conducted on the Randomized Population. Analyses of adverse events (AEs) will include all data collected during the course of the entire 4-week treatment period for each treatment regardless of IP use. Analyses of hypoglycemia and CGM measures will be conducted using the data from first dose to last dose of IP in each 4-week treatment period, and due to the crossover design, treatment comparisons will be based upon the derived outcome variables for Week 2 to 4 in each 4-week treatment period. Analyses of the CareLink report data that are transferred to eCRF (eg, percentage of time spent in Auto Mode, total daily doses during the last 2 weeks) will include all data collected, regardless if patients are temporarily off pump or IP during the 2 weeks or not. Pump-related safety analyses (eg, infusion set changes) will exclude data (if any) that are collected while patients are temporarily off pump or off IP. For analyses of CGM, insulin doses and meal information by infusion set wear day, only data from the infusion sets with ≥ 60 hours (2.5 days) of wear will be included so that adequate data can be used for by-day (Day 1, Day 2, and Day 3) comparison. Data collected during the safety follow-up period will not be used for comparisons between treatments.

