6.10.7. Pump-related Safety Analyses

The protocol requires that patients change infusion set every 3 days, unless a change is required for failure of the infusion set in which case an unplanned infusion set change with noted reason needs to be reported in the patient's study diary and transferred to the eCRF. Accordingly, all infusion set changes captured in the CareLink raw data will be classified into 2 categories: planned and unplanned. An infusion set change will be classified as "unplanned" if there is an unplanned infusion set change reported in eCRF linked by time (within a 12-hour window, considering the fact that the patient-reported infusion set change time for eCRF could be slightly off the precise change time stored in the CareLink raw data). Other infusion set changes will be classified as "planned".

If there are unplanned infusion set changes reported in the eCRF that do not have linked records in the Carelink raw data (potentially due to misreporting), these records will be excluded from the calculation of time until infusion set changes and will be reported in the Electronic Trial

Master File (eTMF) as permanent data issues. To be conservative, these infusion set changes will be still included in the analysis of rate and incidence of unplanned infusion set changes.

The incidence (percent of patients with at least 1 event) and rate will be analyzed using Prescott's exact test and Wilcoxon signed-rank test, respectively for planned, unplanned infusion set changes for any reason and for each individual reason (pump occlusion alarm, unexplained high BG, infusion site reaction [pain, redness or swelling at infusion site], infusion set problem [infusion set kinked, pulled out, leaking, reservoir empty, etc.]), by overall (across all infusion set wear days) and by infusion set wear day (Day 1, Day 2, and Day 3).

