6.10.7.1. Time until Infusion Set Changes

Date and time of all infusion set changes will be captured in the CareLink raw data. Time interval until infusion set change for each infusion set can be derived based upon the CareLink raw data by calculating the time difference (hours) between the infusion set change and its previous infusion set change.

For each treatment period (lead-in, Period I and Period II), time interval until infusion set change (overall, planned, unplanned, or unplanned due to unexplained high BG) will be derived by averaging across the corresponding infusion set changes that occur within the period. The analyses for time interval (overall and planned) will be then conducted by an MMRM model similar to that for the primary endpoint. Time interval until unplanned infusion set change due to unexplained high BG will be summarized by treatment. No treatment comparison will be conducted due to the low occurrence.

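### A set failure handled by stopping the pump, with the new set inserted only on resumption, is missed by exploratory endpoint 10 and may be labelled a planned change

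*SAP*

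**What the plan says.** Endpoint 10 (Protocol section 4, exploratory) compares the rate per 30 days and the incidence of unplanned infusion set changes, by reason, over each 4-week period. The reasons are pump occlusion alarm, unexplained high glucose, infusion site reaction and infusion set problem. The diary is the source, and its entries are transferred to the eCRF.

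Protocol 9.1.4.3 makes one exception to diary entry. When a patient resumes the pump after an interruption, "the infusion set change should not be entered as an unplanned infusion set change in the study diary". The cause of the interruption does not alter this. The interruption is recorded elsewhere: "Any interruption of CSII will need to be documented in the eCRF".

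SAP 6.10.7 sorts all CareLink set changes into two classes. A change is unplanned if an eCRF unplanned record lies within 12 hours of it. "Other infusion set changes will be classified as" planned. One mismatch is provided for: eCRF records "that do not have linked records in the Carelink raw data (potentially due to misreporting") are left out of the interval calculation, but "To be conservative, these infusion set changes will be still included in the analysis of rate and incidence of unplanned infusion set changes".

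SAP 6.10.7.1 derives each set's interval by "calculating the time difference (hours) between the infusion set change and its previous infusion set change". "The analyses for time interval (overall and planned) will be then conducted by an MMRM model". SAP 6.1 says that pump-related safety analyses "will exclude data (if any) that are collected while patients are temporarily off pump or off IP". Table ITSM.6.2 repeats this exclusion in its rows for unplanned set changes and for the time interval.

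**The concern.** The two-class rule presumes that every failure-driven change reaches the diary. The protocol's exception for changes on resumption breaks that presumption, and the SAP does not mention it.

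The sequence is permitted. Protocol 7.7 allows basal, regular or nonstudy rapid-acting insulin for up to 48 hours per treatment period. Protocol 8.2 discontinues a patient only after more than 3 consecutive days without investigational product.

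The SAP's safeguard also runs in one direction. An eCRF record without a CareLink match is counted as unplanned. A CareLink change without an eCRF record is called planned however early it occurs.

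At stake is the by-treatment comparison of set failures. If the resumption changes are not excluded, the planned rate, incidence and interval comparisons are affected too. The listing of unplanned changes (SAP 6.10.7.2) has the same gap, as does the pilot review that draws on it (SAP 6.10.7.4).

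**Working it through.** **Tracing one failure.** A set fails, the patient stops the pump and injects, and a new set goes in only on resumption.

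1. Under Protocol 9.1.4.3 the new set is not entered in the diary as unplanned, so the eCRF holds no unplanned record for it.
2. SAP 6.10.7 finds no link within 12 hours and labels the change planned. An exception arises only if another unplanned record happens to fall inside the window.
3. If the off-pump exclusion (SAP 6.1, Table ITSM.6.2) covers the change or its interval, it is dropped. The wording does not settle whether a change that ends an interruption was collected off pump.
4. On neither reading does the failure enter endpoint 10.

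A failed set that is replaced and entered in the diary before the pump is stopped still counts.

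**Effect per missed event on endpoint 10.** The plan gives no figure to reproduce. Inputs are a 28-day period, a rate per 30 days, and 36 completers or 42 randomized (Protocol 10.1).

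- Patient's rate: 30/28 = 1.07 per 30 days.
- Treatment mean: 1.0714/36 = 0.030, or 1.0714/42 = 0.026.
- Incidence, if it was the patient's only event: 100/36 = 2.8 points, or 100/42 = 2.4 points.
- For an assumed 1, 2 or 3 such patients of 36 on one treatment, incidence is understated by 2.8, 5.6 or 8.3 points and the mean rate by 0.030, 0.060 or 0.089.

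**Effect on the treatment contrast.** If shares f_L (LY900014) and f_H (Humalog) of failures are missed, the observed rate ratio is the true ratio × (1 − f_L)/(1 − f_H). Equal shares leave it unchanged. As an assumed illustration, with 10% to 25% missed on LY900014 only, a true ratio of 1.0 appears as 0.90 to 0.75 and a true 2.0 as 1.8 to 1.5. With the same shares missed on Humalog only, a true 1.0 appears as 1/0.90 = 1.11 to 1/0.75 = 1.33.

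**Effect on mean intervals, if off-pump time is not excluded.** Assume one failure in 28 × 24 = 672 h and all other sets worn for 72 h. With failure at hour F and D hours off pump, the recorded interval is F + D. The number of other sets is R = (672 − F − D)/72, with fractions allowed for simplicity.

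- Mean under the SAP rule, overall and planned alike: 672/(1 + R).
- Overall mean of on-pump wear: (672 − D)/(1 + R), so the overall excess is D/(1 + R).
- Correct planned mean, without the failed set: 72 h, so the planned error is 672/(1 + R) − 72.

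| F (h) | D (h) | SAP mean (h) | Overall excess (h) | Planned error (h) |
|---|---|---|---|---|
| 12 | 24 | 68.3 | 2.4 | −3.7 |
| 12 | 48 | 70.7 | 5.1 | −1.3 |
| 24 | 24 | 69.5 | 2.5 | −2.5 |
| 24 | 48 | 72.0 | 5.1 | 0.0 |
| 48 | 24 | 72.0 | 2.6 | 0.0 |
| 48 | 48 | 74.7 | 5.3 | +2.7 |

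With failure at hour 24 and 48 h off pump, the change at hour 72 looks exactly on schedule. The overall mean is 72.0 h against (672 − 48)/9.333 = 66.9 h of wear, but the planned mean is correct.

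**Early change with no diary entry.** For a change at hour 10, R = (672 − 10)/72 = 9.194, and the patient's planned mean is 672/10.194 = 65.9 h instead of 72 h.

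**The case against.** The loss needs a particular sequence. Protocol 7.2 provides for a set change when a set fails, spare sets are dispensed, and patients are trained to respond to alarms and unexplained hyperglycemia (9.1.4.4). Many failures will be replaced and entered at once. Where the protocol gives examples of CSII interruption (inclusion criterion 5), they are hospitalization, pump malfunction and a pump holiday. For such causes the diary rule properly prevents false unplanned events. All of this stands. A reader might infer that every failure that stops pump use drops out, but the documents do not support that.

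A reader might also infer that planned intervals are inflated by about 5 hours. They are not. The 5.1 h excess concerns the overall mean and arises only if off-pump time is kept, which Table ITSM.6.2 may already rule out. The planned error is negative, zero or positive depending on timing.

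For early changes without a diary entry, the diary is the designated source of the reason and some changes will be for convenience. That argues against moving them into the main count, not against a sensitivity analysis.

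Other safety routes remain: investigator review of alarms and unexplained hyperglycemia at each visit (Protocol 9.1.4.3), infusion site reactions as adverse events (SAP 6.10.4.3), and discontinuation for ketoacidosis (Protocol 8.2). None restores the missing events to endpoint 10.

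**Conclusion.** The point holds, as a minor one. Read together, the two rules leave a failure replaced only on resumption out of endpoint 10, on either reading of the off-pump exclusion. The protocol's diary rule causes the loss. The SAP default does not repair it and may add a wrong planned label. Early changes with no diary entry take the same default.

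The sizes in the working assume 28 days of exposure and, for incidence, no other unplanned change in that patient. The total effect cannot be computed, because the documents do not say how many interruptions follow set failure. A reader might infer a bias for or against LY900014. The documents support no direction, and equal missed shares preserve the rate ratio.

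Endpoint 10 is exploratory, with no multiplicity adjustment. Primary and secondary endpoints are unaffected.

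**What to change.** In SAP 6.10.7, add a third class, *after CSII interruption*: the first CareLink set change after an eCRF interruption record.

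- Keep it out of the planned rate, incidence and interval comparisons, and report it by treatment.
- State that an interval spanning an interruption is excluded, or ended at the start of the interruption if that time was recorded.
- Add a sensitivity analysis of unplanned changes for any reason. It adds this class, by cause where the eCRF records one, and counts unlinked changes with under 60 hours of wear as *early, reason not reported*. Exclude the changes made at site visits.

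The 60-hour limit is borrowed. SAP 6.1 uses it to secure enough data for comparisons by wear day, not to define premature failure.

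The cost is SAP wording and modest programming with eCRF interruption records and CareLink change times. No new assessment is needed, and the primary analysis and alpha do not change. The documents do not show that the eCRF holds the start time or cause of an interruption, so those steps are conditional. If the database is already locked, SAP 6.1 allows such a change to be justified in the clinical study report. The downside is that some added changes will be for convenience or follow interruptions unrelated to failure, so they stay in the sensitivity analysis.

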6.10.7.1. Time until Infusion Set Changes

Date and time of all infusion set changes will be captured in the CareLink raw data. Time interval until infusion set change for each infusion set can be derived based upon the CareLink raw data by calculating the time difference (hours) between the infusion set change and its previous infusion set change.

For each treatment period (lead-in, Period I and Period II), time interval until infusion set change (overall, planned, unplanned, or unplanned due to unexplained high BG) will be derived by averaging across the corresponding infusion set changes that occur within the period. The analyses for time interval (overall and planned) will be then conducted by an MMRM model similar to that for the primary endpoint. Time interval until unplanned infusion set change due to unexplained high BG will be summarized by treatment. No treatment comparison will be conducted due to the low occurrence.

6.10.7.2. Unplanned Infusion Set Changes

A listing of all unplanned infusion set changes will be generated for the Enrolled Population. For each unplanned infusion set change, the following information will be provided:

- the most recent SMBG within 1 hour before the infusion set change measured by the study meter
- the most recent glucose within 1 hour before the infusions set change transferred/entered in the pump
- the 3 most recent CGM values within 20 minutes before the infusion set change
- the reason for the infusion set change
- the infusion set wear day on which the infusion set change occurs
- the infusion set cannula length at screening
- the infusion set cannula length at the time of the infusion set changes

In addition, a listing of unplanned infusion set changes due to unexplained high BG will also be generated. This listing will include the following additional information about the glucose response to the correction boluses, if any, that are delivered as

“CLOSED_LOOP_BG_CORRECTION” within 1 hour prior to the infusion set change, according to the CareLink raw data:

- date and time of the correction bolus
- the most recent SMBG within 1 hour before the correction bolus measured by the study meter
- the most recent glucose within 1 hour before the correction bolus transferred/entered in the pump
- the 3 most recent CGM values within 20 minutes before the correction bolus
- the 3 CGM measures within the time interval of [1 hour -10 minutes, 1 hour +10 minutes] following the correction bolus that were collected prior to the infusion set change
- the most recent SMBG within 1 hour + 10 minutes following the correction bolus measured by the study meter
- the most recent glucose within 1 hour + 10 minutes following the correction bolus transferred/entered in the pump

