7.1.2.3. Pump Alerts

Patients should use the Auto Mode feature of their MiniMed 670G pump as much as possible throughout the trial, including use of the Auto Mode Bolus feature to deliver boluses to cover meals, and whenever the pump recommends a bolus.

Factory set Auto Mode Exit High and Low Sensor Glucose Alerts cannot be silenced and are always enabled when the pump is in Auto Mode.

The pump will exit Auto Mode based on a set SG threshold:

- 300 mg/dL or higher for 1 hour
- 250 mg/dL or higher for 3 hours
- 50 mg/dL or lower for any period of time.

Factory set Low Alert cannot be silenced and is always enabled, whether the pump is in Auto Mode or Manual Mode.

In addition, study site programmed Sensor Glucose Alerts will be standardized for all patients throughout the study. High Alerts will be set to occur when SG reaches >180 mg/dL and Low Alerts will be set to occur when SG reaches <70 mg/dL.

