6.13. CGM Analyses

The analyses described in Section 6.13 will include data collected from first dose to last dose of study drug (ie, open-label Humalog used during the lead-in period or IP used during each of the randomized treatment periods [Period I and Period II]), excluding data (if any) that are collected while patients temporarily are off pump or off study treatment.

All of the variables will be derived for the lead-in period, Period I, and Period II. For the lead-in period, the variables will be derived based upon the data collected during the 2-week open-label Humalog treatment period. For Period I and Period II, the variables will be derived for 0 to 2, 2 to 4, and 0 to 4 weeks relative to the start of each randomized treatment period, respectively. Due to the crossover design, treatment comparisons will be based upon the derived outcome variables for 2 to 4 weeks.

Table ITSM.6.6 lists all numerical measures for CGM data, including all primary, secondary and exploratory CGM outcome variables.

To ensure that the CGM outcome variables are only calculated from CGM session days with sufficient data within the 24-hour, daytime (0600 hours to midnight), or nighttime (midnight to 0600 hours) periods, the following criteria will be used to determine a valid CGM session day to be counted into the calculation for a visit: minimum number of measures per day – at least 70% of the total measures that are supposed to be obtained, i.e. 70% of the 288 measures for the 24-hour period;

Similarly, for the by-meal outcome variables, the following criteria will be used to determine a valid CGM session day for a visit: minimum number of measures per day – at least 70% of the total measures that are supposed to be obtained. For example, 70% of the 24 measures for the iAUC_{0-2hr} after breakfast.

The definition and derivation of these variables are described in detail in [Appendix 1](#).

Table ITSM.6.6. Outcome Measures of CGM Data

Category	Endpoints	24-Hour	Daytime ^a	Nighttime ^b	By Meal ^c
Efficacy Endpoint: Glucose in the Target Ranges					
	Duration (in minutes) and percentage of time with sensor glucose values within target range 70 to 180 mg/dL [3.9 and 10.0 mmol/L], both inclusive (Primary Efficacy Endpoint)	X	X	X	X
	Duration (in minutes) and percentage of time with sensor glucose values within target range 70 to 140 mg/dL [3.9 and 7.8 mmol/L], both inclusive	X	X	X	X

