9.3. Incremental Area under the Glucose Curve (iAUC)

iAUC_{0-T} will be calculated as the average value of iAUC on all valid CGM days during that visit with sufficient data to calculate the iAUC_{0-T} (Section 6.13). For each day, iAUC_{0-T} will be

calculated as the sum of areas of all individual trapezoids within the time frame according to the formula:

$$iAUC_{0-T} = \sum_{i=1}^k A_i = \sum_{i=1}^k \frac{(G_i - G_0) + (G_{i-1} - G_0)}{2} \Delta t_i$$

where A_i is area of the respective trapezoid, G_i is glucose concentration at a particular time, G_0 is the starting glucose concentration before the start of the meal, Δt_i is the time interval between consecutive CGM values, which should be always 5 minutes unless missing data occur, and k is the total number of intervals within the time frame 0-T. If the intermediate time points are missing, the next available time point will be used in calculating the trapezoid area. Also since it is possible that $G_i < G_0$ or $G_{i-1} < G_0$, A_i could also be negative. G_0 , the starting glucose concentration, will be calculated as the average of the CGM values in the time window [-19, 0] mins relative to the start of the meal (at most 3 CGM values); G_k , the last glucose concentration, is defined as the average of the CGM values in the window [0, +14] minutes relative to the last time point of the time frame (at most 2 CGM values). For example, to calculate $iAUC_{0-2hr}$ after the start of breakfast, G_k will be the average of the CGM values in the window [0, +14] minutes relative to the 2 hours after the start of breakfast. The derivation of each $iAUC_{0-T}$ will require that G_0 and G_k values are both available. The derivation $iAUC_{0-T}$ on a specific infusion set wear day, requires that time 0 and time T fall on the same infusion set wear day, but it is acceptable that the CGM measures in the window [-19,0] for G_0 and [0,+14] for G_T fall on the previous or the next infusion set wear day.

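### In the SAP listing of set changes for unexplained high BG, the 1-hour bolus look-back and the 50 to 70 minute CGM response window overlap by at most 10 minutes, so the three requested readings are essentially unobtainable; two companion response items lack a cut-off at the set change

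*SAP*

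**What the plan says.** SAP 6.10.7.2 describes two listings. The first covers all unplanned infusion set changes and gives glucose shortly before each change: the latest SMBG and pump-entered glucose in the prior hour, and the last three CGM values in the prior 20 minutes.

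The second covers changes due to unexplained high BG. "This listing will include the following additional information about the glucose response to the correction boluses, if any, that are delivered as" one type, labelled CLOSED_LOOP_BG_CORRECTION. Only boluses given "within 1 hour prior to the infusion set change, according to the CareLink raw data" enter it. It has seven bolus-level items:

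- Four are the bolus date and time, and SMBG, pump glucose and CGM before the bolus.
- The fifth is the CGM response: "the 3 CGM measures within the time interval of [1 hour -10 minutes, 1 hour +10 minutes] following the correction bolus that were collected prior" (the limit being the set change).
- The sixth is "the most recent SMBG within 1 hour + 10 minutes following the correction bolus measured by the study meter".
- The seventh is the matching item for glucose transferred to or entered in the pump, over the same 70 minutes.

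The sixth and seventh items do not carry the pre-change limit that the CGM item carries.

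On sensor cadence, SAP 9.3 gives the spacing of consecutive CGM values, "which should be always 5 minutes unless missing data occur". SAP 6.13 sets its valid-day rule as "70% of the 288 measures for the 24-hour period".

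**The concern.** The look-back and the response window work against each other. A bolus enters the listing only if the set change follows within an hour, yet its CGM response is sought about an hour later and must still precede the change. Boluses given more than 70 minutes before the change, for which the whole response window would be visible, are excluded.

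The two meter-based items have the opposite problem. Without a cut-off they can pick up a value measured after the new set was in place and show it as the response to a bolus given through the old one.

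The listing has a clear use. Protocol 3.3 notes that high glucose which does not respond to a pump correction may point to an occluded set or a pump problem. SAP Table ITSM.4.1, endpoint 10, labels this reason category as suspected set occlusion. SAP 6.10.7.1 makes no treatment comparison of time to such changes because few are expected, so case-by-case reading carries more weight. SAP Version 3 added the pre-bolus glucose to this listing, which supplies a before value; the matching CGM after value is the one that will usually be missing.

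**Working it through.** **Inputs**

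- Lag L from bolus to set change: 0 to 60 minutes (SAP 6.10.7.2).
- CGM response window: 50 to 70 minutes after the bolus, and before the change (SAP 6.10.7.2).
- Meter and pump-glucose response window: 0 to 70 minutes after the bolus, no cut-off (SAP 6.10.7.2).
- CGM spacing: 5 minutes (SAP 9.3).
- Distribution of L: not in the documents, so assumed and varied below.

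**Cadence reproduced.** 288 measures per day gives 1440/288 = 5 minutes. The 24 measures that SAP 6.13 expects over 2 hours give 120/24 = 5 minutes. Both agree with SAP 9.3.

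**Usable CGM time.** With the bolus at time 0 and the change at L ≤ 60, the usable stretch runs from 50 to min(70, L). Its length is x = max(0, L − 50), so x ≤ 10 of the 20 minutes.

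**Readings obtainable.** With 5-minute spacing and a random starting phase:

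- P(at least 1) = min(1, x/5)
- P(at least 2) = min(1, max(0, (x − 5)/5))
- P(at least 3) = min(1, max(0, (x − 10)/5)) = 0 for every x ≤ 10

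The one exception has probability zero under a random phase: L exactly 60, readings exactly at 50, 55 and 60 minutes, and the reading at the moment of change counted as before it.

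**Averaged over L.** As x goes from 0 to 10, the first probability integrates to 2.5 + 5 = 7.5 minutes and the second to 2.5 minutes.

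| Assumed lags | At least 1 | At least 2 | All 3 |
|---|---|---|---|
| Even over 0 to 60 min | 7.5/60 = 12.5% | 2.5/60 = 4.2% | 0% |
| Triangular, rising to 60 min | 23% | 8% | 0% |
| Even over 30 to 60 min | 7.5/30 = 25% | 2.5/30 = 8.3% | 0% |
| Even over 50 to 60 min | 7.5/10 = 75% | 2.5/10 = 25% | 0% |

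A simulation of 2,000,000 lags per row agrees (0.125, 0.234, 0.250 and 0.750 for at least one) and never produced a third reading. The 75% belongs to an even spread over 50 to 60 minutes. A single bolus 55 minutes or more before the change always has at least one reading (x/5 ≥ 1), but still not three.

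**Meter and pump-glucose items.** Their window ends 70 − L minutes after the change. Since L ≤ 60, it always runs at least 10 minutes past the change. At L = 20, for example, 50 of its 70 minutes fall after the change.

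**Effect of a longer look-back, lags even over W minutes.** Now x = min(L, 70) − 50 where positive. P(at least 1) reaches 1 at L = 55, and P(at least 3) reaches 1 at L = 65.

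| Look-back | At least 1: (2.5 + W − 55)/W | All 3: (2.5 + W − 65)/W |
|---|---|---|
| 2 h (W = 120) | 67.5/120 = 56% | 57.5/120 = 48% |
| 3 h (W = 180) | 127.5/180 = 71% | 117.5/180 = 65% |
| 4 h (W = 240) | 187.5/240 = 78% | 177.5/240 = 74% |

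**The case against.** The strongest reply is that this is one starved field in a descriptive listing and that the information is partly available elsewhere. Much of that stands.

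- A reader might infer that the whole listing will be almost empty. It will not. Only one of the seven bolus-level items is starved; the bolus time, the pre-bolus values and the two meter-based items can be filled.
- A reader might infer that nothing else planned shows the response. The pre-change CGM values partly do. With lags even over 0 to 60 minutes, at least one of those three values falls after the bolus for (2.5 + 55)/60 = 96% of boluses, and all three do for (2.5 + 45)/60 = 79%. They show glucose up to the change, not at a fixed hour. SAP 6.13 also plans individual R Shiny plots of CGM with doses and set changes, without a look-back limit.
- A reader might infer that endpoint 10 is compromised. The reason for a change comes from the patient's diary (Protocol 9.1.4.3), and SAP 6.10.7 tests rate and incidence from recorded changes. The listing feeds neither test.
- A reader might infer that Manual Mode corrections are lost: the pump leaves Auto Mode at "300 mg/dL or higher for 1 hour", and "Unexplained hyperglycemia is defined as high BG >300 mg/dL". But neither document defines the label CLOSED_LOOP_BG_CORRECTION, corrections in the first hour can still fall in Auto Mode, and no loss can be quantified. This is a question to check, not a finding.
- The missing cut-off is softened because the last SMBG and pump glucose before the change are listed for the same event. One could also read the post-bolus items as meaning the latest value before the change, but the text does not say so, and the CGM item beside them does.

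None of this lets the CGM response field hold what it asks for.

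**Conclusion.** The point holds, at low severity. As written, the CGM response field cannot hold its three readings. That follows from the two windows and the 5-minute cadence alone and needs no assumption about bolus timing, apart from the exact-boundary coincidence. How often the field holds anything does depend on timing: 12.5% with lags even over the hour, up to 75% with lags even over its last 10 minutes. These are assumed scenarios, not predictions.

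The absence of a cut-off on the post-bolus SMBG and pump-glucose items is a matter of wording, and the possible overrun is at least 10 minutes for every eligible bolus. How often a value is actually taken in that overrun cannot be known from the documents.

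The effect is confined to case-level interpretation of set changes for unexplained high BG.

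**What to change.** In SAP 6.10.7.2:

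1. Lengthen the bolus look-back beyond 70 minutes so that the response window can close before the change, and list each bolus with its time before the change. Two to 4 hours is an example range; the documents do not fix the length.
2. Keep the 50 to 70 minute CGM window and its pre-change limit, and say which three readings to list, since a full 20-minute window normally holds 20/5 = 4.
3. Limit the post-bolus SMBG and pump-glucose items to values collected before the infusion set change.
4. Optionally, establish what CLOSED_LOOP_BG_CORRECTION covers. If it is Auto Mode only, also list Manual Mode corrections with a mode flag.

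The cost is SAP wording and listing code. SAP 5.1 and 6.10.7 already draw the pump-related outcomes from the CareLink raw data, so no new collection is needed. The downside is a longer listing that may include some earlier corrections unrelated to the change; showing the time before the change lets the reader discount them.
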